2.4.5.6 Subgroup analyses

Subgroup analyses will be performed for several key safety variables (treatment-emergent AE/SAE/AESI/AE leading to permanent treatment discontinuation) by:

- ICS dose group: patients on the medium or high ICS dose at the original baseline in parent studies
- Age group (< 18, 18-64, \geq 65 years)
- Race (Caucasian/White, Black/of African descent, Asian/Oriental, all the other)
- Sex (Female, Male)
- Ethnicity (Hispanic, Not Hispanic)

2.4.6 Analyses of pharmacokinetic and pharmacodynamic variables

The baseline value of PK and PD variables is the original baseline from the parent studies.

2.4.6.1 Pharmacokinetic analysis

The PK analyses will be performed on the PK population (Section 2.3.4). Serum concentrations of dupilumab will be summarized using arithmetic and geometric means, SD, standard error of the mean (SEM), coefficient of variation (CV), minimum, median and maximum by visit. If date and/or time of the drug intake and/or sampling are missing, then the concentration will not be taken into account. For the patients from the Dupilumab arms of EFC13579, EFC13691 or PDY14192 studies,, if the pre-dose concentration values at Week 0 of LTS12551 are below the lower limit of quantitation (LLOQ = 78 ng/ml), one-half of LLOQ will be used; for the patients from the Dupilumab arms of DRI12544 study, the pre-dose concentration value at Week 0 of LTS12551 should use 0; for the patients from the Placebo arms of parent studies, the pre-dose concentration value at Week 0 of LTS12551 should use 0 of LTS12551 should use 0 of LTS12551 should use 0. Values will be expressed in the tables with no more than three significant figures.

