11.3.3 Pharmacokinetics population

The PK population (the systemic drug concentration population) will consist of all the patients in the safety population with at least one non-missing and evaluable predose serum concentration value after the first dose of dupilumab in the LTS12551 study.

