11.4.4 Analyses of pharmacokinetic and pharmacodynamic variables

11.4.4.1 Pharmacokinetic analysis - (drug concentration analyses)

The PK analyses will be performed on the PK (systemic drug concentration) population. The baseline value of each applicable PK variable is the original baseline from the parent studies.

Serum concentrations of functional dupilumab will be summarized using arithmetic and geometric means, SD, standard error of the mean (SEM), coefficient of variation, median, minimum and maximum per visit.

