2.1.5 Pharmacokinetic variables

Blood samples of serum functional dupilumab are collected at Visit 1, Visit 4 (Week 4), Visit 8 (Week 12), Visit 11 (Week 24), Visit 13 (Week 48; if applicable), Visit 15 (Week 72; if applicable), Visit 17 (End-of-Treatment), Visit 18 (End-of-Study) and/or early termination, and before the IMP administration at corresponding scheduled visits that are specified in the protocol. The pre-dose serum dupilumab concentration will be collected at the scheduled visits in LTS12551 study. The baseline values for PK variables are the original baselines from the parent studies.

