2.3.4 Pharmacokinetics (PK) population

The PK population will consist of all the patients in the safety population who had at least one non-missing functional dupilumab concentration value after the 1st dose of study drug in the current study.

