		Taiget day	Minimum days	Maximum days	Minimum days	Maximum days	
1&2	0	Derived		1 st IMP dose date/time (Day 1)		1 st IMP dose date/time (Day 1)	
3	2	15			2	21	
4	4	29			22	35	
5	6	43			36	49	
6	8	57			50	63	
7	10	71			64	77	
8	12	85	2	126	78	98	
9	16	113			99	126	
10	20	141			127	154	
11	24	169	127	252	155	210	
12	36	253			211	294	
13	48	337	253	420	295	378	
14	60	421			379	462	
15	72	505	421	546	463	546	
16	84	589	547	630	547	630	
17 (EOT)	96	673	631	d*	631	d*	
18 (EOS)	108	757	d*+1		d*+1		

*Note: d= max (last dose +14 days, EOT date)

For the pharmacokinetics/pharmacodynamics variables summary, the reference date for the derivation of relative days of measurements will be the date of first IMP dose injection in LTS12551 study. Pharmacodynamics variables will be summarized by the analysis window defined in Table 7 for the by visit descriptive analyses. All available values of scheduled measurements will be assigned to the appropriate visit window. In the event of multiple measurements of the same test in the same window, the one closest to the targeted visit date will be used for the by-visit summary. If they are at the same distance to the target day, the latest one will be used. The pre-dose measurements at Week 0 of LTS12551 are defined in the same way as in the paragraph prior to Table 5.

Vieit	Visit Week Target day		PK sampling, dupilu	imab concentration	Anti-drug antibodies		
VISIC			Minimum days	Maximum days	Minimum days	Maximum days	
1 & 2	0	Derived		Up to 1st IMP dose date/time		Up to 1st IMP dose date/time	
3	2	15					
4	4	29	After 1st IMP dose date/time	56			
5	6	43					
6	8	57					
7	10	71					
8	12	85	57	126	After 1st IMP dose date/time	126	
9	16	113					
10	20	141					
11	24	169	127	252	127	252	
12	36	253					
13	48	337	253	420	253	420	
14	60	421					
15	72	505	421	588	421	588	
16	84	589					
17 (EOT)	96	673	589	d*	589	d*	
18 (EOS)	108	757	d*+1		d*+1		

Table 7 - Time window for pharmacokinetics and pharmacodynamics variables

*Note: d= max (last dose +14 days, EOT date)

Visit	Week	Target	et Total IgE		
Viole	Hook	day	Minimum days	Maximum days	
1 & 2	0	Derived		Up to 1st IMP dose date/time	
3	2	15			
4	4	29			
5	6	43			
6	8	57			
7	10	71			
8	12	85			
9	16	113			
10	20	141			
11	24	169			
12	36	253			
13	48	337	After 1st IMP dose date/time	462	
14	60	421			
15	72	505			
16	84	589	463	630	
17 (EOT)	96	673	631		
18 (EOS)	108	757			

*Note: d= max (last dose +14 days, EOT date)

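### The PK by-visit summary has no time-since-last-dose rule, so samples from dosing interruptions or a late EOT visit count as on-treatment, while a missing clock time alone discards a dated value

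*SAP*

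**What the plan says.** PK sampling is planned before dosing. SAP 2.1.5 states: "The pre-dose serum dupilumab concentration will be collected at the scheduled visits in LTS12551 study". Protocol 11.4.4.1 plans that "Serum concentrations of functional dupilumab will be summarized using arithmetic and geometric means", with the median among the other by-visit statistics. SAP 2.4.6.1 plans the same statistics and adds one exclusion for single values: "If date and/or time of the drug intake and/or sampling are missing, then the concentration will not be taken into account". Neither section limits the time since the last dose.

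SAP 2.5.4, Table 7, places scheduled PK samples in windows counted from the first LTS12551 dose. If a window holds several samples, the one nearest the target study day is kept. The EOT row ends at d and the EOS row starts the day after, where "d= max (last dose +14 days, EOT date").

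The PK population differs between the documents. Protocol 11.3.3 asks for "at least one non-missing and evaluable predose serum concentration value after the first dose of dupilumab in the LTS12551 study". SAP 2.3.4 asks for "at least one non-missing functional dupilumab concentration value after the 1st dose of study drug in the current study". Evaluable is not defined in either, and the SAP's lists of changes (1.5 and 1.6) do not mention the difference.

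**The concern.** Systemic exposure is a stated secondary objective, and a reader of the by-visit table will take the Week 4 to EOT rows as concentrations under every-2-week dosing. If those rows also hold values from patients who had paused or stopped, the mean and geometric mean are pulled down, and an apparent fall over time could be read as declining exposure. The same concentrations feed the optional ADA-by-PK exploration in SAP 2.4.7.5, where an interruption could resemble an antibody effect. SAP section 3 puts all planned analyses into the interim report for the asthma submission.

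The one stated exclusion does not address this. It removes values for an incomplete time stamp, including values whose time since dose is known to within a day, and leaves in values that are weeks from a dose.

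**Working it through.** **1. Reproduce the Table 7 windows.** Target day = 7 × week + 1, giving 29, 85, 169, 337, 505 and 673 for Weeks 4, 12, 24, 48, 72 and 96. Midpoints between neighbours: (29+85)/2 = 57, (85+169)/2 = 127, (169+337)/2 = 253, (337+505)/2 = 421, (505+673)/2 = 589. The windows therefore end on days 56, 126, 252, 420 and 588, exactly as printed. Widths are 56, 70, 126, 168 and 168 days. Dosing is every 14 ± 3 days (Protocol 8.1.3), so a planned pre-dose sample lies 11 to 17 days after the previous dose.

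**2. Late EOT after early discontinuation.** The flow-chart footnotes ask for a prompt EOT visit but give no maximum delay. Take the last dose on day 141, so last dose + 14 = 155:
- EOT day 155: d = 155, 14 days post-dose
- EOT day 169: d = 169, 28 days post-dose
- EOT day 200: d = 200, 59 days post-dose
- EOT day 252: d = 252, 111 days post-dose

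From day 155 on, d equals the EOT date, so the EOT sample can never fall after d. All four lie in the Week 24 window (127 to 252). If the patient also had a day-169 sample, that one would be kept instead. The problem arises when the EOT sample is the only one in the window, or the one nearest the target.

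**3. Interruptions.** Protocol 10.3.1 allows temporary discontinuation and gives no maximum length in that section. With a dose on day 113, the next three missed, and a Week 24 sample on day 169, the sample is 169 − 113 = 56 days post-dose and sits on the Week 24 target day. No stated rule flags it.

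**4. EOS overlap.** In the 48-week cohort the last dose is day 7 × 46 + 1 = 323, so d = 337. EOS is day 337 + 84 = 421 (414 to 428 with the ± 1 week window), 98 days post-dose. It belongs to the EOS row (from day 338) but also lies in the Week 48 range (to 420) or the Week 72 range (from 421). Table 7 states no precedence.

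**5. Clock time.** If both dates are known and differ by n days, the elapsed time lies between n − 1 and n + 1 days. That is within the protocol's own ± 3 day dosing tolerance, yet SAP 2.4.6.1 drops the value.

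**6. Sensitivity, on assumed inputs only.** The documents give no half-life, trough level, interruption rate or EOT delay. SAP 1.5 says only that the median was below 78 ng/mL 12 weeks after the last dose on 300 mg q2w in DRI12544. Let f be the share of off-interval samples in a row (assumed). Case A sets them at 25% of the typical on-schedule value. Case B sets them at half the LLOQ, 0.039 mg/L (a rule that the SAP gives only for Week 0), with a typical on-schedule value T of 10 to 100 mg/L. The geometric mean (GM) is multiplied by 0.25^f in A and (0.039/T)^f in B. The arithmetic mean (AM) in A is multiplied by 1 − 0.75f. If all off-interval values are low, the overall median is the (0.5 − f)/(1 − f) quantile of the on-schedule samples.

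| f | GM fall, A | GM fall, B | AM fall, A | Median sits at |
|---|---|---|---|---|
| 1% | 1.4% | 5.4% to 7.5% | 0.75% | 49.5th percentile |
| 5% | 6.7% | 24% to 32% | 3.75% | 47.4th percentile |
| 10% | 12.9% | 43% to 54% | 7.5% | 44.4th percentile |

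The table shows only that the geometric mean is the fragile statistic and the median moves little. It is not an estimate for this trial.

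**The case against.** The strongest case on the other side is that limits already exist. Samples are planned before dosing, only scheduled measurements enter the windows, EOT is planned 2 weeks after the last dose, and post-treatment samples have their own row. The study is single-arm and descriptive, the median is reported, and summarising exposure as observed, interruptions included, is a legitimate choice. Restricting to on-schedule samples conditions on adherence. All of this stands. It narrows the gap to interruptions and late EOT visits, and it is why the all-samples summary should stay beside the filtered one.

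Several stronger readings are tempting and are not supported:
- A reader might infer that dropping the evaluable-predose condition causes the mixing. It does not. Both definitions are met by a single value, so a patient with one valid Week 4 sample qualifies under either and all later samples follow. The protocol has no sample-level rule either. Its visit schedule even labels the EOT and EOS samples predose, so the words alone would not settle which samples count.
- A reader might infer that the ± 7 day visit window routinely gives samples 7 days early. At on-treatment PK visits through Week 72 a dose follows the sample, and doses must be at least 11 days apart, so a compliant pre-dose sample is at most 3 days early. A larger shift is plausible mainly at EOT.
- The objective says systemic exposure, not steady state, and SAP 2.4.6.1 uses pre-dose only for Week 0, so the plan does not label its on-treatment means as troughs.
- Heavy loss of home-dosed values is not shown. Sampling date and time come from the laboratory form (Protocol 9.3.1.1) and home injections have their own record pages (8.1.3). How often a clock time is missing is unknown.

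**Conclusion.** The point holds in limited form. No stated rule keeps concentrations taken during a dosing interruption, or at a late early-discontinuation EOT visit, out of the on-treatment rows, and the definition of d ensures that a late EOT sample is never treated as post-treatment. A value with known dates can be discarded for a missing clock time. The unlisted difference between SAP 2.3.4 and Protocol 11.3.3 is real but separate: it bears only on PK population membership. The missing precedence for EOS samples in Table 7 is a related gap. The size of any distortion cannot be computed from the documents, and the table above rests wholly on assumed inputs. This is an inexpensive improvement to a secondary, descriptive analysis and does not touch the primary safety endpoint.

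**What to change.** Four changes to SAP wording:
1. Align SAP 2.3.4 with Protocol 11.3.3 and define evaluable.
2. In 2.4.6.1, for the post-Week 0 on-treatment rows only (Week 4 to EOT), base the main by-visit summary on samples within a stated time since the last dose. For example, use 11 to 17 days, from the protocol's 14 ± 3, with EOT samples allowed 14 ± 7 = 7 to 21 days for the visit window. Show the all-samples summary and a listing by days since last dose alongside. Leave Week 0 and EOS outside the filter: EOS is planned 98 days after the last dose and would be emptied, and at Week 0 former placebo patients have no previous dupilumab dose while DRI12544 patients had a gap of at least 16 weeks.
3. Exclude values for missing dates only. Require clock time only when dose and sample fall on the same day.
4. State in Table 7 that the EOS row takes precedence over the fixed-day windows for samples after d.

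The cost is a somewhat smaller n in the main on-treatment summary, by an amount that the documents cannot give. Dose and sample dates are already collected, so no new data are needed.

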1.4.1 Graphical Study Design

1.5 MODIFICATIONS TO THE STATISTICAL SECTION OF THE PROTOCOL

Amendment Number	Date Approved	Rationale	Description of statistical changes
4	31-Oct- 2016	Based on the data defining the safety profile of dupilumab to date (as determined in multiple clinical trials performed across the AD, Asthma and NP indications), data from a 1 year asthma OLE study is anticipated to be sufficient to support the asthma program.	The open-label treatment duration is amended to 48 weeks (1 year), for patients providing consents after the implementation of the protocol amendment 4.
4	31-Oct- 2016	The DRI12544 study showed that the median dupilumab concentration at 12 weeks post-last-dose (at PK steady-state) was below the limit of quantitation (78 ng/mL) for the group of patients on 300 mg every 2 weeks (q2w). Given this, the duration of study participation can be minimized by reducing the post-treatment period by 1 month. The follow-up duration for all the ongoing dupilumab asthma studies has been harmonized as 12 weeks.	The post-treatment period is shortened to 12 weeks for all patients in the LTS12551 study.
4	31-Oct- 2016	The patient population from study EFC13691 is a different population from the patient population from the other parent studies. The patients from	Three efficacy endpoints linked to the prescribed oral corticosteroids (OCS) dose and corresponding analyses have been added only for the patients from the EFC13691.

Table 1 - Protocol amendment statistical changes

Amendment Number	Date Approved	Rationale	Description of statistical changes
		EFC13691 are more severe at the baseline of the parent study and are using a different background controller medication. The endpoints linked to the reduction of the OCS dose are only used in EFC13691, in addition to the other efficacy endpoints shared in common with the patients from the other parent studies.	

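### The Week 0 zeros in the PK rules defeat the required geometric mean, the DRI12544 zero ignores any measured value, and nothing is said about values below quantitation after Week 0

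*SAP*

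**What the plan says.** **Statistics required.** SAP 2.4.6.1: "Serum concentrations of dupilumab will be summarized using arithmetic and geometric means", with SD, SEM, CV, minimum, median and maximum, by visit. Protocol 11.4.4.1 agrees: "Serum concentrations of functional dupilumab will be summarized using arithmetic and geometric means".

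**Week 0 substitution (SAP 2.4.6.1).** Three clauses follow one another:
- Dupilumab arms of EFC13579, EFC13691 and PDY14192: if Week 0 values "are below the lower limit of quantitation (LLOQ = 78 ng/ml), one-half of LLOQ will be used".
- DRI12544 dupilumab arms: "the pre-dose concentration value at Week 0 of LTS12551 should use 0".
- All placebo arms: "for the patients from the Placebo arms of parent studies, the pre-dose concentration value at Week 0 of LTS12551 should use 0".

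Only the first clause depends on the measured value.

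**Definition of Week 0.** SAP 2.1 and 2.5.4 take the DRI12544 Week 0 value from that study's End-of-Study visit or, failing that, from the last measurement before the first LTS12551 dose. SAP 2.5.4 extends this definition to the PK variables, and SAP 2.1.5 lists a PK sample at Visit 1.

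**After Week 0.** PK is sampled up to End-of-Study (SAP 2.1.5). Neither the missing-data section (2.5.3) nor the PK window table (2.5.4, Table 7) says how to treat a value below LLOQ. SAP 1.5 reports from DRI12544 that "the median dupilumab concentration at 12 weeks post-last-dose (at PK steady-state) was below the limit of quantitation (78 ng/mL") in the 300 mg q2w group.

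**The concern.** The geometric mean is computed on the log scale and needs positive values, so a rule that inserts zeros cannot sit beside a requirement to report it. The DRI12544 clause raises a second problem: read literally, it replaces a laboratory result with 0 even when that result was quantifiable. Third, End-of-Study is the visit where values below LLOQ should be most common, and no convention is fixed for it.

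Systemic exposure is a secondary objective, and SAP 2.4.7.5 may relate concentration to ADA status using the same values. SAP section 3 foresees interim reports, including one for the asthma submission that runs every planned analysis. With no written convention, the choice could be made after the data are seen, or could differ between reports.

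**Working it through.** **1. LLOQ.** Protocol 9.3.1.3 gives 0.078 mg/L. 0.078 × 1000 = 78 ng/mL, which matches SAP 2.4.6.1. LLOQ/2 = 39 ng/mL.

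**2. Effect of a zero.** Geometric mean = exp(mean of ln x). Because ln 0 is minus infinity, one zero makes the result 0, or incalculable in software that rejects it. CV = SD/mean; in an all-zero group this is 0/0.

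Applied to the layout in SAP 2.3.2, at Week 0:
- Geometric mean and CV both fail: every Placebo/Dupilumab column and the DRI12544 columns (all values 0).
- Geometric mean fails: the non-OCS All column and the EFC13691 All column (zeros mixed with other values).
- Geometric mean usable: Dupilumab/Dupilumab in EFC13579, EFC13691 and PDY14192 only.

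**3. How many zeros.** Sizes and allocation ratios are from SAP 1.1. Assume that every parent-study patient rolls over and enters the PK population, which is an upper bound.
- DRI12544, all arms: 776.
- EFC13579 placebo: 1902 × 2/6 = 634.
- PDY14192 placebo: 42 × 1/2 = 21.
- Non-OCS total: 776 + 634 + 21 = 1431 of 776 + 1902 + 42 = 2720, or 52.6%.
- EFC13691 placebo: 210 × 1/2 = 105 of 210, or 50%.

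If only half of DRI12544 rolled over and everyone else did, the non-OCS figure would be (388 + 634 + 21)/(388 + 1902 + 42) = 1043/2332 = 45%.

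**4. DRI12544 values at risk.** Dupilumab-arm patients number at most 776 × 4/5 ≈ 621. The documents do not give the share with a quantifiable Week 0 value. If it were 5% to 30% (assumed), 31 to 186 measured values would be replaced by 0.

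**5. End-of-Study.** The End-of-Treatment visit is 2 weeks after the last dose and End-of-Study is 12 weeks later (Protocol 10.1.1.16 and 10.1.1.17; the same in 10.1.2.12 and 10.1.2.13). So End-of-Study falls 2 + 12 = 14 weeks after the last dose. A median below 78 ng/mL at 12 weeks, on the regimen that every LTS12551 patient receives, implies that about half or more of the End-of-Study samples are below LLOQ.

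If those values were excluded, every retained value would be at least 78, so the geometric mean would be at least 78 ng/mL with no distributional assumption. To show the spread between conventions, assume lognormal concentrations with 50% to 80% below LLOQ and a log-SD of 1.0 to 2.0 (simulated, 400,000 draws; none of these inputs is in the documents):

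| Share below LLOQ | Log-SD | Geometric mean, LLOQ/2 (ng/mL) | Geometric mean, excluded (ng/mL) | Ratio |
|---|---|---|---|---|
| 50% | 1.0 | 82 | 173 | 2.1 |
| 50% | 2.0 | 122 | 384 | 3.1 |
| 80% | 1.0 | 50 | 137 | 2.7 |
| 80% | 2.0 | 56 | 239 | 4.3 |

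Check of the first row: the mean of a standard normal above its median is 0.798, so the excluded figure is 78 × exp(0.798) = 173, and the LLOQ/2 figure is √(39 × 173) = 82.

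**The case against.** Several points on the other side are sound.

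- A reader might infer that the Week 0 PK summaries as a whole are wrong. They are not. Arithmetic mean, SD, SEM, median, minimum and maximum can all be computed with zeros. For a patient who received placebo in the parent study, 0 is a sensible pre-dose value, and a geometric mean there carries no exposure information. The defect is confined to the geometric mean, and to CV in all-zero groups.
- A reader might infer that many real DRI12544 measurements would be lost. The documents do not show this. The reported median comes from the highest DRI12544 regimen, and by Week 0 these patients had been off drug for 16 weeks or more (SAP 1.1), which is longer than the 12 weeks behind that median. Few values were probably quantifiable. The clause also follows one that does have a below-LLOQ condition, so the author may have meant the condition to carry over. It is not written, however, and the conflict with SAP 2.1 and 2.5.4 stands.
- A reader might infer that the SAP plans to drop End-of-Study values below LLOQ, or to set them to 0. It does neither. SAP 2.4.6.1 excludes concentrations only for missing dosing or sampling dates or times, and it states zeros only for Week 0. LLOQ/2 already appears in the same paragraph and could be the intended convention. The point is silence, not a planned bias.
- The 53% is an upper bound. The protocol synopsis expects about 2206 patients against the SAP maximum of 2930. The share also matters little, since one zero is enough.

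**Conclusion.** The point holds in a limited form. Followed as written, SAP 2.4.6.1 gives a Week 0 geometric mean that is 0 or incalculable in every column except Dupilumab/Dupilumab of EFC13579, EFC13691 and PDY14192. This follows from the text alone and needs no assumption about roll-over.

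The unconditional DRI12544 zero contradicts the SAP's own Week 0 definition. Its numerical effect is unknown and probably small.

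The missing rule after Week 0 is a gap rather than an error. It matters most at End-of-Study, where the geometric mean could differ about 2.1- to 4.3-fold between LLOQ/2 and exclusion under the assumed distributions. That range rests on the lognormal assumption and on DRI12544 behaviour carrying over to this study.

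These are descriptive secondary tables. The primary TEAE endpoint is untouched.

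**What to change.** Amend SAP 2.4.6.1 as follows:

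1. Keep every measured concentration at or above LLOQ, including DRI12544 Week 0 values.
2. For dupilumab-exposed patients, apply the existing LLOQ/2 rule (39 ng/mL) to values below LLOQ at all visits, including DRI12544 dupilumab arms at Week 0 and everyone at End-of-Study.
3. Keep 0 for placebo-arm patients at Week 0, but show no geometric mean or CV for them, and leave them out of any pooled Week 0 geometric mean, with a footnote saying so.
4. Report n (%) below LLOQ at each visit.

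The cost is SAP wording and table shells, with no new data. The drawback is that LLOQ/2 is only approximate when most values are below LLOQ: once more than half are, the End-of-Study median is simply the substituted 39 ng/mL. At that visit the median and the n (%) below LLOQ should be read before the geometric mean.
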